
## Introduction

Extubation is the removal of the endotracheal tube (ETT) when it is no longer required [1]. This procedure may be associated with complications, such as desaturation, stridor, bronchospasm, and severe cough [2,3]. The complication rates reported in the literature range from 6.6% to 100% [4–6]. In some cases, these complications may lead to extubation failure [7].

Two orotracheal extubation (OTE) techniques are described in the literature [8]. The traditional extubation technique consists of introducing a suction catheter into the ETT and trachea, deflating the cuff, and removing the ETT by applying continuous endotracheal suctioning during the entire procedure. The positive pressure extubation technique, on the other hand, involves applying positive pressure through the airway during cuff deflation and extubation. Thus, the air flow passing between the ETT and the larynx pushes pooled subglottic secretions towards the oropharynx so that they can be expelled through the oral cavity. Both techniques intend to minimize the leakage of the oropharyngeal content into the distal airway. However, according to several authors, the negative pressure generated by suctioning during the traditional technique may promote rather than prevent leakage [9,10].

A noninferiority clinical trial showed that the positive pressure extubation technique was safe and noninferior to the traditional technique in terms of the incidence of immediate postextubation complications, postextubation pneumonia (PEP), OTE failure, and reintubation [11]. Although prior studies reported better clinical outcomes with the positive pressure extubation technique [6,12], its superiority has not been deeply studied yet. Therefore, the objective of our study is to determine whether the positive pressure OTE technique, compared with the traditional OTE technique, reduces the incidence of major postextubation complications (up to 60 minutes) in critically ill adult patients.

## Methods

### Design

A multicenter randomized clinical trial was conducted in 13 centers from Argentina. Patients admitted to the intensive care units (ICU) between April 1, 2019, and March 26, 2020, were included in the analysis. Our study was evaluated and approved by the Research Ethics Committee (#12-2018-05, approved on February 28, 2019) and registered on ClinicalTrials.gov (NCT03918811, April 18, 2019). The results were reported according to the CONSORT Statement for reporting randomized clinical trials [13].

### Participants

We included patients aged > 18 years, requiring invasive mechanical ventilation (IMV) through an ETT, who had successfully completed a spontaneous breathing trial (SBT) [14] and met the following OTE criteria: an adequate level of consciousness (Glasgow Coma Scale score  $\geq 8/15$ ) [15] and effective cough (cough at order and/or at endotracheal suctioning) [16,17]. The participants' or their legal representatives' informed consent was also required. Patients with a history of upper airway (UA) injury or surgery, with a limited therapeutic effort, who had previously been extubated or tracheostomized, or who had required noninvasive mechanical ventilation (NIMV) as a weaning method were excluded from our study.

### Procedure and Interventions

Patients who met the eligibility criteria and successfully completed the SBT were immediately randomized. Once OTE was performed by two operators, assessment of outcome measures within 60

min after extubation was done by a third operator (blinded). Daily monitoring of outcome measures within 72 h after extubation was performed by this same operator. If preventive NIMV or high flow nasal cannula (HFNC) had been decided, they were initiated 15 min after OTE in order not to influence monitoring of outcome measures. Extubation maneuvers were performed in accordance with the procedure reported in the literature [11]. The traditional OTE technique consisted of deflating the cuff and removing the ETT by applying continuous endotracheal suctioning during the entire procedure. In positive pressure extubation, ventilator parameters were set at 15/10 cmH2O, in PC-CSV mode. The cuff was deflated, and a suction catheter was introduced through the mouth to suction secretions from the oropharyngeal cavity [11,18,19] while the ETT was removed without endotracheal suctioning (see supplementary material).

### Outcome measures

Postextubation overall complications:[11] clinical evidence of desaturation [3,5,6,20], hypertension [1,3,4,20], tachycardia [1,3,4,20], tachypnea [1,21], or poor respiratory mechanics [21] (at least one within 15 min after extubation), or clinical evidence of UA obstruction [4,22], postobstructive pulmonary edema [2,22], vomiting [3,5], bronchospasm [3,5], or severe cough [3,5,23] (at least one within 60 min after extubation).

Postextubation major complications:[11] clinical evidence of desaturation (within 15 min after extubation), or clinical evidence of UA obstruction or vomiting (at least one within 60 min after extubation).

Postextubation minor complications:[11] clinical evidence of hypertension, tachycardia, tachypnea, or poor respiratory mechanics (at least one within 15 min after extubation), or clinical evidence of postobstructive pulmonary edema, bronchospasm, or severe cough (at least one within 60 min after extubation).

Postextubation pneumonia (PEP) was defined as the presence of new or increased pulmonary infiltrate on chest radiography before OTE, in addition to the presence of fever, leukocytosis ( $> 10,000/\text{mm}^3$ ), or

leukopenia (< 4,000/mm^3) compared with preextubation values and/or increase of tracheobronchial secretions or change in their quality (within 72 h after extubation) [16].

Extubation failure was defined as the need for NIMV or HFNC to treat the failure or reintubation within 72 h after extubation [1,24]. Reintubation was defined as the need for a new introduction of the ETT within 72 h after extubation [1,25].

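### The postextubation pneumonia definition places its only radiographic criterion on a film taken before extubation

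*Combined protocol and SAP*

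**What the plan says.** Methods, Outcome measures, gives PEP one imaging criterion: "the presence of new or increased pulmonary infiltrate on chest radiography before OTE, in addition to the presence of fever", or a raised or lowered white cell count. The sentence goes on: "compared with preextubation values and/or increase of tracheobronchial secretions or change in their quality (within 72 h after extubation) [16". The comparison with pre-extubation values is attached to the fever and white cell items, not to the film, and the 72-hour window comes only at the end.

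The two other 72-hour outcomes in the section are timed plainly. Extubation failure is "the need for NIMV or HFNC to treat the failure or reintubation within 72 h after extubation", and reintubation is "the need for a new introduction of the ETT within 72 h after extubation".

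Methods, Procedure and Interventions, describes the follow-up: "Daily monitoring of outcome measures within 72 h after extubation was performed by this same operator". Methods, Statistical analysis, commits to relative risks and absolute risk differences with 95% confidence intervals for primary and secondary outcomes alike.

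**The concern.** A film taken before extubation cannot show an infiltrate that developed after it. As written, the definition fixes part of the outcome before the randomized technique has been applied.

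This matters because PEP is one of the outcomes through which the technique is expected to act. The Introduction says the earlier noninferiority trial compared the techniques "in terms of the incidence of immediate postextubation complications, postextubation pneumonia (PEP), OTE failure, and reintubation", and gives the rationale: "Both techniques intend to minimize the leakage of the oropharyngeal content into the distal airway". An infiltrate already present before the tube is removed cannot result from leakage during removal. If centers followed the text, PEP status would be wrong for some patients, and the reported PEP effect estimates would carry that error.

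**Working it through.** The plan gives no figure for PEP, so there is none to reproduce. The check compares texts.

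**1. Timing of each outcome definition (Methods, Outcome measures)**

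| Outcome | When its elements are timed |
|---|---|
| Overall complications | within 15 or 60 min after extubation |
| Major complications | within 15 or 60 min after extubation |
| Minor complications | within 15 or 60 min after extubation |
| PEP | film before extubation; closing window 72 h after |
| Extubation failure | within 72 h after extubation |
| Reintubation | within 72 h after extubation |

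Five of the six place every element after extubation. PEP alone has a qualifying element before it.

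**2. Can the closing 72-hour window rescue the sentence?** There are two readings.
- The window governs the whole sentence. The infiltrate must then be on a film taken before extubation and also fall within 72 h after it, which is a contradiction.
- The window governs only the secretions item. The film then has no post-extubation timing at all.

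**3. Does another section settle it?** Radiography and infiltrate are each mentioned once in the supplied text, both in this sentence. The follow-up wording in Methods and in the Supplementary Material gives the 72-hour monitoring, and the supplementary Procedure gives a pre-extubation checklist. Neither names a film.

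**4. Could the literal rule apply to enrolled patients?** Yes. The exclusions in Methods, Participants, are "Patients with a history of upper airway (UA) injury or surgery, with a limited therapeutic effort, who had previously been extubated or tracheostomized", plus noninvasive ventilation used for weaning. An existing infiltrate is not among them.

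**5. Who is classified differently?** Take patients who meet the clinical signs:

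| Group | New or increased infiltrate before extubation | New or increased infiltrate after extubation | Literal rule | Evident intent |
|---|---|---|---|---|
| A | yes | no | case | not a case |
| B | no | yes | not a case | case |
| C | yes | yes | case | case |
| D | no | no | not a case | not a case |

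Write A₁, B₁, C₁ for the proportions of all randomized patients in these groups under positive pressure, and A₀, B₀, C₀ under the traditional technique.
- Literal risk difference = (A₁ − A₀) + (C₁ − C₀)
- Intended risk difference = (B₁ − B₀) + (C₁ − C₀)
- Error = (A₁ − A₀) − (B₁ − B₀)

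None of these proportions is in the document, so neither the size nor the sign of the error can be computed.

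**6. Does it reach the primary analysis?** No. The 778 patients (389 per group) rest on major complication rates of 37.6% and 28.2%. No PEP rate enters that calculation.

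**The case against.** The strongest reply is that this is a slip of the pen that any trained evaluator would read correctly. New or increased implies a baseline, the outcome is named postextubation, the next items in the sentence are compared with pre-extubation values, and outcomes were monitored daily for 72 hours. Together these suggest one sensible meaning: an infiltrate after extubation, judged against the earlier film. The cited source for the definition, or the study forms mentioned in the Supplementary Material, may state the rule properly. Even under literal coding, randomization would balance pre-existing infiltrates in expectation and the evaluator was blinded.

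Much of this stands. The intended meaning is probably as described, no miscoding is shown, and differential assessment is unlikely to be the main risk. The count of five in six is supporting context; the words that place the film before extubation carry the point.

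Two things remain. First, inferring the intent does not show what rule 13 centers applied, and the cited source and forms are not available here. Second, randomization balances infiltrates present beforehand (the film part of group A) but does not recover the cases in group B, which are the ones the technique might affect. Blinding does not make a faulty case definition valid, nor does it guarantee equal misclassification in the two arms.

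**Conclusion.** The concern holds: the PEP definition is wrong as written, and it should be corrected. Confidence is high about the wording. Whether any result is affected is unknown. If coding followed the evident intent, only the sentence is wrong. If it followed the text, PEP status is misclassified, and with it the relative risk and risk difference, by an amount and in a direction the document does not allow one to state. That the fault is a dropped comparator phrase is an inference. The consequence is confined to PEP; the primary outcome in the first hour and the sample size do not depend on it.

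**What to change.** 1. Reword the criterion: an infiltrate that is new or increased on a chest radiograph obtained within 72 hours after extubation, compared with the last film before extubation. In the same edit, group the clinical signs with explicit AND/OR, since the present string of alternatives can be parsed in more than one way.
2. State how PEP was actually coded, including which films were compared.
3. Only if coding followed the literal wording: reclassify PEP under blinding where post-extubation films exist, report the number per arm without such a film, and label the result post hoc.

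The first two steps cost one sentence and one statement. The third requires re-reading films, which may not exist for every patient. The PEP count may change, and some patients may not be classifiable. Because the admission window closed on March 26, 2020, any reclassification can only be post hoc.

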#### Randomization

Randomization was performed in blocks and stratified by participating center and by the risk of extubation failure (high or low), as reported in prior studies [16,26]. Randomization assignment was blinded to the operators in charge of the procedures through an online platform (see supplementary material).

#### Blinding

Due to the nature of the intervention, blinding of patients and operators performing OTE was not possible. The evaluator who recorded measures of interest after extubation was blinded to the assigned extubation technique. The database was monitored by third parties with no direct participation in the study and no interest in its outcomes. The data were analyzed pursuant to the statistical analysis plan devised before the study, and the person in charge of data statistical analysis was blinded to the technique used.

#### Sample size

Based on a major complication rate of 37.6%, reported in a prior study [11], 778 patients (389 per group) were required to have an 80% chance of detecting, as significant at the 5% level, a decrease in

the incidence of major complications from 37.6% in the control group (traditional technique) to 28.2% in the experimental group (positive pressure technique) (relative difference of 25%).

### Statistical analysis

The primary analysis of outcomes was a per-protocol analysis. An intention-to-treat analysis was also performed. Thus, a “worst case scenario” method was adopted, assigning the event of interest to the patients lost to follow-up who were randomly assigned to the positive pressure group and not allocating the event of interest to the patients lost to follow-up who were randomly assigned to the traditional group. No interim analyses were planned. Chi-square test or Fisher exact test were used for the comparison categorical variables. Continuous variables with normal distribution were presented as mean and standard deviation (SD) and were compared with the Student's t test for independent samples. Non-normally distributed variables were presented as median with 25% and 75% percentiles. For outcome measures (primary and secondary), relative risks (RR) and 95% confidence intervals (CI) were calculated. Effect estimates were also reported with their absolute risk differences (ARD) and their corresponding 95% confidence intervals (95% CI). Tests were two-tailed, and a p-value  $<0.05$  was considered significant. Statistical analysis was performed using SPSS version 25.0; SPSS Inc, Chicago, IL, USA.

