### Procedure

Patients were included in the study once they had successfully completed the SBT and met the OTE criteria. The blinded evaluator followed a preextubation checklist. It entailed discontinuing enteral nutrition, adjusting the head of the bed to 45°, suctioning oropharyngeal and tracheobronchial

secretions, and recording preextubation monitoring on the pertaining sheet. Regardless of the procedure, the alarms were silenced, and the ventilator parameters were set at PS 15/10 cmH2O by one operator, so that the blinded evaluator could not hear the maneuver or read the ventilator parameters. The blinded evaluator left and was replaced by the operators, who knew about the technique assigned. They initiated the randomization through <http://extubar.ajrpt.com> and were in charge of the OTE and postextubation oxygen delivery. Regardless of the OTE technique, the patients received supplemental oxygen through a nasal cannula placed before ETT removal to keep the oxygen flow used in the SBT.

Once the OTE was completed, the blinded evaluator assessed the outcome measures recorded within 60 min after extubation. Daily monitoring of outcome measures within 72 h after extubation was carried out.

The decision to perform OTE and to use NIMV or HFNC to prevent OTE failure, follow-up, and treatment was taken by the blinded evaluator, or the respiratory therapist on duty, who was blinded to randomization assignment. If preventive NIMV or HFNC had previously been decided, it was implemented 15 min after OTE so as not to affect monitoring of outcome measures.

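### A superiority trial takes its primary answer from the per-protocol set and puts intention-to-treat second, so the headline comparison is not protected by randomisation

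*Combined protocol and SAP*

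**What the plan says.** The Statistical analysis section sets the order of the analyses: "The primary analysis of outcomes was a per-protocol analysis. An intention-to-treat analysis was also performed". For the second of these it adds a worst-case rule for missing outcomes, "assigning the event of interest to the patients lost to follow-up who were randomly assigned to the positive pressure group", with no event assigned to patients lost from the traditional arm. Tests are two-tailed at 5%.

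The Introduction describes the earlier trial as the noninferiority trial and gives this trial's aim as to "determine whether the positive pressure OTE technique, compared with the traditional OTE technique, reduces the incidence of major postextubation complications". The Sample size section gives 389 patients per group, who "were required to have an 80% chance of detecting, as significant at the 5% level", a fall from 37.6% to 28.2%. No noninferiority margin appears anywhere.

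On conduct, the Blinding section says that "blinding of patients and operators performing OTE was not possible". The supplementary Procedure section says: "The blinded evaluator left and was replaced by the operators, who knew about the technique assigned". The outcome evaluator and the analyst were blinded, and the analysis plan is said to predate the study.

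**The concern.** A per-protocol set is chosen after randomisation. In a noninferiority trial there is a reason to give it prominence, because non-adherence pulls the arms together and can favour the conclusion. That reason does not apply to a superiority question, and no section offers another.

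There is a practical route to bias. The two techniques involve different steps: continuous endotracheal suction in one, set ventilator pressures with oral suction in the other. Staff who know the allocation perform them. A patient who is unstable or has heavy secretions may be more likely to be handled outside the assigned technique, and more so in one arm. If such patients leave the positive pressure arm, the estimate moves towards benefit; if they leave the traditional arm, it moves against benefit. The trial's declared conclusion would then partly reflect who was removed.

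**Working it through.** **Inputs.** From the Sample size section: control risk 37.6%, experimental risk 28.2%, 389 per arm, 80% power, 5% level. From Statistical analysis: two-tailed tests. The documents give no rate of departure from technique and no exclusion count, so the exclusion fraction *x* (2%, 5%, 10%) and the event risk *r* among those excluded (50%, 60%, 70%) are assumptions.

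**1. The plan's own figure.** With unpooled variance and no continuity correction:

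n = (1.96 + 0.8416)² × [0.376×0.624 + 0.282×0.718] / 0.094² = 7.849 × 0.4371 / 0.008836 = 388.3, rounded up to 389 per arm, 778 in total. This matches. A pooled-variance z test at 389 per arm has power 79.8%. The concern is not about arithmetic.

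**2. Bias from exclusions in one arm when there is no true effect.** Both arms have risk 37.6%. A fraction *x* is removed from the positive pressure arm only. The risk in those retained is

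retained risk = (0.376 − x·r) / (1 − x),

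and the spurious absolute risk difference (ARD) is this minus 0.376. The two-sided error is

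Φ[(d − 1.96·SE₀)/SE₁] + Φ[(−d − 1.96·SE₀)/SE₁],

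where d is the size of the ARD, SE₀ the pooled and SE₁ the unpooled standard error, with 389 and 389(1 − x) patients.

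Example, x = 5% and r = 60%: (0.376 − 0.030)/0.95 = 0.3642, ARD = -1.18 points; SE₀ = 0.0351, SE₁ = 0.0351; error = Φ(−1.62) + Φ(−2.30) = 6.3%.

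| Excluded (about, of 389) | r = 50%: ARD / error | r = 60%: ARD / error | r = 70%: ARD / error |
|---|---|---|---|
| 2% (8) | -0.25 / 5.06% | -0.46 / 5.20% | -0.66 / 5.41% |
| 5% (19) | -0.65 / 5.39% | -1.18 / 6.30% | -1.71 / 7.75% |
| 10% (39) | -1.38 / 6.72% | -2.49 / 10.78% | -3.60 / 17.43% |

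ARD is in percentage points. A simulation with 400,000 trials per cell gave errors of 5.0–5.4%, 5.3–7.6% and 6.7–17.5% for the three rows. The same exclusions from the traditional arm give the mirror image, +0.3 to +3.6 points with the same errors. Equal exclusions at equal risk in both arms leave the error at 5.0%.

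**3. Power under each analysis at the planned effect.** If a fraction *x* of the positive pressure arm received the traditional technique, the intention-to-treat risk in that arm is 0.282 + 0.094x. If the same fraction were instead excluded at random, the per-protocol comparison has 389 against 389(1 − x) patients.

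| x | Intention-to-treat power | Per-protocol power |
|---|---|---|
| 2% | 78.1% | 79.4% |
| 5% | 75.5% | 78.7% |
| 10% | 70.7% | 77.6% |

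**4. The worst-case rule at the planned effect.** If a fraction *d* is lost in each arm (assumed), the control risk becomes 0.376(1 − d) and the experimental risk 0.282(1 − d) + d. For d = 1%, 2% and 5% the ARD moves from -9.4 to -8.3, -7.2 and -3.9 points. The rule is a stress test and would be a poor primary estimate.

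**The case against.** The strongest case is that there was little room for departures. Operators start randomisation at the bedside once the breathing trial, the extubation criteria and the checklist are complete. The intervention is one short procedure that centres were trained in by video, and the primary outcome ends at 60 minutes. If nobody was excluded, the two analysis sets are the same. The 10% one-sided row, which supplies the 17.4% figure, is then the least plausible. Where the excluded patients' risk is closer to the base rate (30–45%), the same formula gives errors of only about 5.02%, 5.15% and 5.6% at 2%, 5% and 10% excluded. Intention-to-treat is also planned, with a rule that counts losses against the new technique, and the blinding and prior plan limit steering by results.

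Most of this stands as mitigation. The harm is conditional, and it may be small. But the short procedure is an inference from design and not a count of departures. Blinding of the evaluator and analyst does not balance a subset formed after allocation. The worst-case rule deals with loss to follow-up in the secondary analysis and does nothing for exclusions in the primary one. A null intention-to-treat result could also be dismissed as a product of that rule.

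The supplied text does not define the per-protocol set. Little should be made of that, since the text is short and refers to a separate plan.

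**Conclusion.** The concern holds. The order of analyses is wrong for a superiority question, and nothing in the documents reverses or justifies it. How far the result is affected cannot be found from the documents. Under the stated assumptions (no true effect, one-sided exclusions, 50–70% risk among those excluded) the false difference is 0.3 to 0.7 points at 2% excluded, 0.7 to 1.7 at 5% and 1.4 to 3.6 at 10%, in either direction, with two-sided error of 5.1–5.4%, 5.4–7.7% and 6.7–17.4%. The bias is small at 2%, nil if exclusions are unrelated to outcome, and material only if they are more frequent, uneven between arms and related to risk. It still needs correcting, because the choice of analysis set decides the trial's headline conclusion.

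**What to change.** - Make intention-to-treat primary: every randomised patient, in the arm assigned, with the observed outcome. Report patients without a recorded outcome by arm and reason.
- Keep the worst-case rule as a sensitivity analysis.
- Keep per-protocol as supportive, state its definition, and list exclusions by arm and reason.
- The Design section describes a completed trial, with patients admitted "between April 1, 2019, and March 26, 2020, were included in the analysis". A change made after the data were seen must be disclosed as post hoc, with both results shown.

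**Cost.** No new data should be needed. Intention-to-treat on observed outcomes is a variant of the planned analysis, which is described with worst-case imputation, so one further run is required. Non-adherence may dilute the estimate, and power is somewhat lower than per-protocol in the scenarios above. The gain is protection from selection bias, not power.

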## Randomization

The randomization sequence was generated before the study by using the web site (<https://www.sealedenvelope.com/>) in blocks of 6 and stratified by participating center and by the risk of extubation failure (high or low). High risk of extubation failure was defined as the presence of at least one of the following criteria: age  $\geq 66$  years, moderate or severe chronic obstructive pulmonary disease (COPD),  $\geq 2$  comorbidities (COPD, peripheral artery disease, immune deficiency, liver disease, hypertension, diabetes, neurological disease, heart failure, chronic renal failure), body mass index (BMI)  $\geq 31$ , congestive heart failure as main reason from IMV, difficult intubation, IMV  $\geq 8$  days, a requirement of suctioning respiratory secretions ( $\geq 3$  suctions within 4 h before the OTE), difficult or prolonged

weaning and/or APACHE II (*Acute Physiology and Chronic Health disease Classification System II*) a day before the OTE  $\geq 13$ . Randomization assignment was blinded to researchers in charge of recruiting patients through an online platform (<http://extubar.ajrpt.com>).

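### The randomisation strata (13 centres by extubation-failure risk) are not used in the stated analysis, so precision is forgone if centre or risk predicts the outcome

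*Combined protocol and SAP*

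**What the plan says.** **Design and allocation.** Methods, Design: "A multicenter randomized clinical trial was conducted in 13 centers from Argentina". Supplementary Material, Randomization, says the sequence was generated "in blocks of 6 and stratified by participating center and by the risk of extubation failure (high or low"). Methods, Randomization, names the same two factors. Thirteen centres times two risk levels is 26 strata, or 778 / 26 ≈ 30 patients each on average.

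**Analysis.** Methods, Statistical analysis: "Chi-square test or Fisher exact test were used for the comparison categorical variables". For effect sizes, "For outcome measures (primary and secondary), relative risks (RR) and 95% confidence intervals (CI) were calculated", and absolute risk differences with 95% confidence intervals are added. The section names no stratified test, regression model, or adjustment for centre or risk, and no other section does.

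**Sample size.** Methods, Sample size: "778 patients (389 per group) were required to have an 80% chance of detecting, as significant at the 5% level", for a fall "from 37.6% in the control group (traditional technique) to 28.2% in the experimental group (positive pressure technique").

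**The concern.** Blocking within strata forces the arms to be nearly balanced on centre and risk. If either factor is related to the outcome, the difference between arms varies less over repeated randomisations than it would under simple randomisation. A standard error from the pooled two-by-two table does not know this and still includes the between-stratum variation. The confidence intervals then come out wider than the design warrants, and the test rejects a true null hypothesis less than 5% of the time.

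Only precision is at stake. The direction of the error is safe, but the stratified design makes extra precision available that the stated analysis leaves unused.

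It is plausible, though not shown, that the strata matter. The risk criteria were defined for extubation failure, which is itself a secondary outcome; a link with major complications (desaturation, upper airway obstruction, vomiting) is not documented. Centres could differ in how the breathing trial was run, since several methods and durations were allowed, and in how bedside events were judged.

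**Working it through.** **1. Inputs from the document.** 37.6% vs 28.2%, 389 per group, 80% power and 5% level (Sample size); two-tailed tests (Statistical analysis); 13 centres (Design); two risk levels and blocks of 6 (Supplementary Material, Randomization).

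**2. The plan's own figure.** Unpooled two-proportion formula, per group:

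n = (1.960 + 0.842)² × [p₁(1−p₁) + p₂(1−p₂)] / (p₁−p₂)²

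- p₁(1−p₁) = 0.376 × 0.624 = 0.2346
- p₂(1−p₂) = 0.282 × 0.718 = 0.2025
- sum = 0.4371; difference squared = 0.094² = 0.008836
- n = 7.849 × 0.4371 / 0.008836 = 388.3, rounded up to 389

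The 778 therefore reproduces, and it is the size of an unstratified comparison. (The pooled formula gives 392 per group.)

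**3. Effect of ignoring the strata.** Let s be the patient-weighted between-stratum SD of the event rate. The document does not give it, so s is an assumption and is varied.

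- Variance used by the crude analysis: 0.4371 / 389
- Variance under stratified blocking: (0.4371 − 2s²) / 389
- Crude 95% half-width: 1.96 × √(0.4371/389) = 1.96 × 0.03352 = 6.57 points
- Interval ratio: √[0.4371 / (0.4371 − 2s²)]
- Equivalent patients: 778 × [0.4371 / (0.4371 − 2s²) − 1]

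Example, s = 0.10: 0.4371 − 0.02 = 0.4171; half-width 1.96 × √(0.4171/389) = 6.42 points; ratio 1.024; 778 × (0.4371/0.4171 − 1) = 37 patients.

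| s | Stratum rates, if uniform around 33% | Stratified half-width (points) | Interval ratio | Power points forgone | Crude test size | Equivalent patients |
|---|---|---|---|---|---|---|
| 0 | all equal | 6.57 | 1.000 | 0 | 5.0% | 0 |
| 0.05 | 24–42% | 6.53 | 1.006 | 0.3 | 4.9% | 9 |
| 0.10 | 16–50% | 6.42 | 1.024 | 1.3 | 4.5% | 37 |
| 0.15 | 7–59% | 6.22 | 1.056 | 2.8 | 3.9% | 89 |
| 0.20 | very large variation | 5.94 | 1.106 | 4.9 | 3.0% | 174 |

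**4. Simulation check.** 10,000 runs per scenario: 26 strata, uneven centres, 60% high risk (assumed), permuted blocks of 6, uniform stratum effects; crude z-test against Cochran-Mantel-Haenszel (CMH).

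| s | Interval ratio | Power, crude / CMH | Size, crude |
|---|---|---|---|
| 0 | 0.999 | 80.5% / 80.5% | 4.9% |
| 0.05 | 1.004 | 80.0% / 80.0% | 4.8% |
| 0.10 | 1.022 | 80.0% / 81.3% | 4.7% |
| 0.15 | 1.054 | 80.3% / 83.2% | 4.1% |

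The size of the CMH test was 4.9–5.2%, and the bias of either risk difference was at most 0.04 points. With about 4 of 26 strata below 10 patients, Mantel-Haenszel risk-difference intervals (Sato variance) covered 94.6–95.4%. Monte Carlo standard error is about 0.2 points for size and 0.4 for power.

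**5. A second parameterisation.** Here 6,000 runs per scenario used a between-centre SD on the logit scale and an odds ratio for high vs low risk, with 50% high risk and marginal rates held at the plan's values.

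| Centre SD / risk OR | Power, crude / stratified | Size, crude |
|---|---|---|
| 0 / 1 | 79.5% / 79.3% | 4.6% |
| 0.3 / 1.5 | 79.0% / 79.8% | 4.9% |
| 0.5 / 2 | 80.7% / 82.4% | 4.3% |
| 0.8 / 2 | 81.4% / 84.8% | 3.8% |
| 0.8 / 3 | 82.2% / 86.3% | 3.3% |

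In the last scenario the crude model-based standard error is 0.0333 against a true 0.0318, so the interval is 0.0333 / 0.0318 ≈ 1.05 times as wide as it need be.

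**6. A rarer outcome** (assumed 10% vs 7.5%): the interval is 0.1% too wide at s = 0.02 and 0.9% at s = 0.04, with about 0.5 power points or less forgone.

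**The case against.** The case for leaving the plan alone is reasonable. The trial was sized as an unstratified comparison and analysed as one, so the plan is consistent. The test is valid and at worst slightly conservative. No document shows that centre or risk predicts major complications, and a gain of even 1.3 points needs strata running from about 16% to 50%. All of this stands, and it is why the point concerns efficiency only.

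Four further objections can be answered in whole or in part.

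- **Sparse strata.** Any one of a long list of criteria makes a patient high risk, so the high-risk share may be well above 50–60%. With 90% assumed, about 10 or 11 of the 26 strata fall below 10 patients. In that setting CMH loses at most a fraction of a power point, within simulation noise, when the strata are uninformative, and keeps its gain when they are informative. One set of runs at 90% found little gain up to s = 0.08 (80.4% crude, 80.5% CMH), in line with the small gains expected there.
- **Per-protocol primary analysis.** Exclusions after randomisation disturb the balance within strata. With 8% random exclusions (assumed) the result is unchanged. Sato coverage across these checks, including a rarer outcome, was 94.4–95.9%.
- **Rare secondary outcomes.** The gain is very small there. This limits the benefit but does no harm.
- **Timing.** The document is written in the past tense, after recruitment ended. A stratified analysis added once crude results are known must be labelled as such. That affects how it is presented; it does not change the mismatch between design and analysis.

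**Conclusion.** The concern holds. The design stratifies by centre and risk, and the stated analysis ignores both. The consequence is a conditional and modest loss of precision. It is nil if the strata do not predict the outcome, negligible at a between-stratum SD of 0.05, about 2% in interval width and 1.3 power points at 0.10, and 5–6% and about 3 points at 0.15. Only very large variation (SD 0.20, by formula alone) brings it to about 11% and 4.9 points.

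These figures rest on assumed stratum effects, centre sizes and high-risk share, because the document gives none of them. What is certain is the omission and the direction of its effect. The risk difference is not biased and the planned 80% power is not undercut. The change is still worth making because it costs almost nothing even when the strata turn out to be uninformative.

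**What to change.** For the primary and secondary binary outcomes, in both the per-protocol and intention-to-treat analyses, state a Cochran-Mantel-Haenszel test stratified by centre and extubation-failure risk. Report the Mantel-Haenszel common risk ratio and risk difference with 95% confidence intervals from variance estimators that remain valid in sparse strata: Greenland-Robins for the ratio and Sato for the difference. Keep the crude table and the crude RR and ARD as descriptive results. If the crude results are already known, say plainly that the stratified analysis was added afterwards.

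The cost is a change of wording in the analysis plan and minor programming. Centre and risk stratum were needed to randomise each patient, so no new data are required.
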